4.2 Scientific Rationale for Study Design

This Phase 2 basket study uses a sequential monitoring procedure to assess the antitumor activity of lenvatinib in children, adolescents, and young adults with relapsed/refractory malignancies for which there are no standard therapy regimens. The sequential monitoring design allows enrollment of a limited number of participants to determine drug activity, thereby preventing exposure of participants to a drug that is inactive for the specific tumor type. The safety of lenvatinib will be evaluated at the RP2D of single-agent lenvatinib (14 mg/m²), as determined in Study 207.

4.2.1 Rationale for Endpoints

4.2.1.1 Efficacy Endpoints

This study will use ORR, defined as the proportion of participants with confirmed objective response (an objective response of CR or PR at Week 16, based on RECIST 1.1 or RANO for HGG as assessed by the investigator) as the primary endpoint. For single-arm studies, ORR is commonly used to assess clinical activity of therapies in the treatment of pediatric solid tumors. The use of RECIST 1.1 and the use of RANO for HGG to assess ORR is typically considered acceptable by regulatory authorities.

Antitumor activity for participants with neuroblastoma enrolled in the other solid tumors' cohort will be determined by the following criteria and combined with RECIST-based efficacy for assessment of the study endpoints.

- CR: Complete resolution of all MIBG-positive lesions.
- PR: Resolution of at least 1 MIBG-positive lesion, with persistence of other MIBG-positive lesions.
- SD: No changes in MIBG scan in number of positive lesions.

- PD: Development of new MIBG-positive lesions.

DOR, BOR over the treatment period, DCR, CBR, and PFS are secondary endpoints that will serve as additional measures of efficacy and are commonly accepted endpoints by both regulatory authorities and the oncology community.

Overall survival, defined as the time from the first day of study intervention to death due to any cause, will be an exploratory endpoint.

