5.1 Inclusion Criteria

A participant will be eligible for inclusion in the study if the participant:

Type of Participant and Disease Characteristics

1. Has histologically or cytologically documented relapsed, or refractory pediatric solid malignancy excluding osteosarcoma.
Participants with diffuse midline glioma (formerly known as diffuse intrinsic pontine glioma), optic pathway glioma, or pineal tumors with elevated tumor markers (AFP, β -hCG, or hCG) do not require histological or cytological confirmation of diagnosis. Participants with diffuse midline glioma are not eligible for the HGG cohort and should only be enrolled in the other solid tumors' cohort.
2. Has measurable disease as defined by RECIST 1.1 or RANO for HGG, meeting the criteria below:
 - All tumor types except HGG and neuroblastoma: At least 1 lesion measuring ≥ 1.0 cm in the longest diameter for a non-lymph node or ≥ 1.5 cm in the short-axis diameter for a lymph node that is reproducibly measurable on CT or MRI scans.
 - HGG: At least 1 contrast-enhancing lesion with clearly defined margins on T1-weighted MRI scan, measuring ≥ 1.0 cm in 2 perpendicular diameters, and visible on at least 2 axial slices (preferably no more than 5 mm apart with 0 mm gap).
 - Participants with neuroblastoma who do not have measurable disease per RECIST 1.1 but have MIBG-positive evaluable disease may be enrolled.
 - Tumor lesions situated in a previously irradiated area or in an area subjected to other locoregional therapy are considered measurable only if progression has been observed in such lesions since the completion of therapy.

3. Has a performance status as defined below:

- Lansky Play Score ≥ 50 for participants up to and including 16 years of age.
- KPS ≥ 50 for participants >16 years of age.
- Neurologic deficits in participants with primary CNS tumors must have been stable for at least 7 days prior to study enrollment. Participants who are unable to walk because of paralysis, but who can perform ADL while wheelchair bound, will be considered ambulatory for the purpose of assessing the performance score.

4. Demonstrate adequate organ function as defined below:

System	Laboratory Value																				
Hematological																					
For participants without bone marrow involvement																					
ANC	$\geq 1000/\mu\text{L}$																				
Platelets	$\geq 75,000/\mu\text{L}$																				

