8.2.1.1 Initial Tumor Imaging

Initial tumor imaging at Screening must be performed within 28 days prior to the date of allocation. Tumor imaging performed as part of routine clinical management is acceptable for use as screening tumor imaging if it is of diagnostic quality and performed within 28 days prior to the date of allocation.

Participant eligibility will be determined based on confirmation by the investigator that the participant has measurable disease per RECIST 1.1 for all tumor types except for HGG, which will be evaluated per RANO criteria. In addition, participants with neuroblastoma who do not have measurable disease per RECIST 1.1 but have MIBG-positive evaluable disease may be enrolled (see Section 4.2.1.1).

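### Neuroblastoma response is to be judged by MIBG and counted in the study endpoints, but the readable analysis text does not carry this through, and one MIBG scan can be both PR and PD

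*Combined protocol and SAP*

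**What the plan says.** Section 4.2.1.1 defines the primary response as "an objective response of CR or PR at Week 16, based on RECIST 1.1 or RANO for HGG as assessed by the investigator". It then gives separate MIBG categories for neuroblastoma in the other solid tumors' cohort, to be "combined with RECIST-based efficacy for assessment of the study endpoints". Two of those categories matter here: "PR: Resolution of at least 1 MIBG-positive lesion, with persistence of other MIBG-positive lesions" and "PD: Development of new MIBG-positive lesions". No order of precedence is given.

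Inclusion criterion 2 in Section 5.1 opens with "Has measurable disease as defined by RECIST 1.1 or RANO for HGG, meeting the criteria below". Its lesion-size bullet reads "All tumor types except HGG and neuroblastoma: At least 1 lesion measuring" and so exempts neuroblastoma. A further bullet says "Participants with neuroblastoma who do not have measurable disease per RECIST 1.1 but have MIBG-positive evaluable disease may be enrolled". Section 8.2.1.1 repeats this and points back to Section 4.2.1.1.

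The evaluable definition (Sections 1.1 and 4.1), the EAS definition (9.1 and 9.5.1) and the ORR evaluability sentence (9.6.1) all require measurable disease at baseline. None makes an exception for MIBG. Section 4.1 says ORR is assessed by RECIST 1.1 in every tumor type but HGG. Sections 3, 9.1, 9.4.1, 9.6.1 and Table 5 likewise name only RECIST 1.1 or RANO.

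**The concern.** The protocol sets up a route into the study and a way of scoring response for neuroblastoma, and the analysis sections then appear not to know about either. An analyst who follows Section 9 to the letter leaves out treated participants whose responses Section 4.2.1.1 says to count. An analyst who follows Section 4.2.1.1 to the letter can score as PR a scan that shows a new lesion. Two competent programmers could therefore produce different numerators, denominators and PFS dates from the same data. In an open-label study the choice between them may be made after the responses are known.

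**Working it through.** There is no plan figure to reproduce: the question is whether the texts agree, and Sections 9.7.2 and 9.9 are redacted.

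**1. Who is in the primary population.** Take a neuroblastoma participant with MIBG-positive disease and no RECIST-measurable lesion.
- Sections 5.1 and 8.2.1.1: eligible.
- Section 4.2.1.1: MIBG response counts toward the study endpoints.
- Sections 1.1, 4.1, 9.1, 9.5.1 and 9.6.1: measurable disease required, so on a literal reading not evaluable and not in the EAS.
- Section 5.5: a participant who is not evaluable is replaced.

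**2. Which criteria apply.** Take any neuroblastoma participant, with or without measurable disease.
- Section 4.2.1.1: MIBG categories, combined with RECIST.
- Section 4.1 (all types but HGG), Section 3, Section 9.1 (primary endpoint row), 9.4.1, 9.6.1, Table 5 and the ORR sentence of 4.2.1.1 itself: RECIST 1.1 or RANO only.

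This conflict does not depend on what counts as measurable. No readable text says how MIBG and RECIST results combine in a participant who has both.

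**3. Do the MIBG categories exclude one another?** Baseline lesions A and B; at follow-up A is gone, B is still positive and C is new.
- CR: not met, because B is positive.
- PR: at least one resolved (A) and others persisting (B). Met.
- PD: a new lesion (C). Met.
- SD: the count is 2 − 1 + 1 = 2, unchanged, so SD is also met if it is read as a net count.

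The PR/PD overlap is general: it occurs whenever at least one baseline lesion resolves, at least one persists and at least one new lesion appears. For HGG, Table 10 in Appendix 8 avoids this by making any new lesion PD.

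**4. Consequence for PFS.** PFS is a study endpoint and runs to the first documentation of PD. If the MIBG criteria apply to it, the scan in step 3 could be the response date for ORR and the event date for PFS.

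**5. One illustration. The counts are assumed; the documents give none.** Suppose 6 neuroblastoma participants are treated, 2 of them MIBG-only, with 1 RECIST responder and 1 MIBG-only responder. The exact limits are the Clopper-Pearson limits the plan specifies: lower = Beta⁻¹(0.025; x, n − x + 1), upper = Beta⁻¹(0.975; x + 1, n − x).
- Section 9 read literally: n = 6 − 2 = 4, x = 1; 1/4 = 25.0% (0.6 to 80.6).
- MIBG-only participants in the EAS but only RECIST responses counted: 1/6 = 16.7% (0.4 to 64.1).
- Section 4.2.1.1 applied in full: 2/6 = 33.3% (4.3 to 77.7).

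With counts this small, the reading chosen moves the estimate, though all three intervals overlap widely.

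**The case against.** The strongest reply is that Section 4.2.1.1 is the specific rule and should govern the general text. The MIBG bullet sits under the measurable-disease criterion, neuroblastoma is exempted from the lesion-size bullet, the disease is called evaluable, and Section 8.2.1.1 cross-refers to Section 4.2.1.1. On that reading MIBG-only participants are in the EAS. This is arguable, so a reader should not infer that they are certainly excluded. Against it, criterion 2 ties measurability to RECIST 1.1 or RANO, and the bullet describes people who lack RECIST-measurable disease. Even if the reply is accepted, steps 2 and 3 stand.

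A reader might also infer that false responses will be confirmed under the MIBG rules. That goes too far. Confirmation needs a second scan at least 4 weeks later, and Section 8.2.1.2 continues imaging only until the investigator identifies progression. If the new lesion is called PD, no confirming scan is assured.

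Finally, a rule may exist where this review could not look: Sections 9.7.2 and 9.9 are redacted, and the imaging manual (SIM) and supplemental SAP (sSAP) were not available. The sections that define populations, endpoints and methods are readable, however, and contain no MIBG rule.

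**Conclusion.** The plan is inconsistent as written. Section 4.2.1.1 and the readable analysis text cannot both be followed for neuroblastoma, and the MIBG PR and PD definitions can both be met by one scan. The criteria conflict and the overlap are certain on the text; the exclusion of MIBG-only participants is the literal reading, not the only one.

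The reach is limited to neuroblastoma participants already in the other solid tumors' cohort, where Sections 1.1 and 4.4 say further enrollment was discontinued. The number affected is not given and may be zero, so the effect cannot be sized. HGG, RMS, EWS/pPNET and the safety set are untouched. It would be tempting to infer that the decision to stop enrolling that cohort was affected; nothing in the documents links that decision to MIBG classification. The point merits correction before the primary analysis but does not threaten the study's main conclusions.

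**What to change.** **(a) Reconcile the texts.** State whether MIBG-only participants belong to the primary EAS. If they do, extend the evaluable/EAS wording in 1.1, 4.1, 9.1, 9.5.1 and 9.6.1 to neuroblastoma with at least one MIBG-positive lesion at baseline, and name the MIBG criteria wherever RECIST or RANO is now named alone: the objectives (1.1 and 3), both the ORR-assessment and site-assessment sentences of 4.1, the ORR sentence of 4.2.1.1, 9.1, 9.4.1, 9.6.1 and Table 5. If they do not, amend 4.2.1.1. The evaluable definition also drives replacement and the 9-participant interim trigger, so this is not purely an analysis edit; closed enrollment makes that side largely moot.

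**(b) Remove the overlap.** For endpoint classification, let a new MIBG-positive lesion (PD) take precedence over CR, PR and SD, in line with Table 10, and state how MIBG and RECIST results combine in a participant who has both.

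**(c) Show the choice.** Report ORR with and without MIBG-only participants, and MIBG-based and RECIST-based responses separately.

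Sections 8.2.1.4 and 7.1 also rest progression and stopping of study intervention on RECIST 1.1 outside HGG. Those responsible for the protocol must reconcile them with Section 4.2.1.1; no clinical rule is proposed here.

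The cost is wording and one extra table line. Some PRs may be reclassified as PD.

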The primary objective of the study is to evaluate ORR at Week 16 for each cohort separately as assessed per RECIST 1.1 or RANO (for HGG) by the investigator. On-study imaging assessments will be performed at screening, every 8 weeks from the date of lenvatinib initiation until Week 24, then every 12 weeks thereafter, or as clinically indicated (± 7 days). All responses will be confirmed at a follow-up examination ≥ 28 days after the initial response. Images will be collected by a central imaging vendor for possible independent review of response; site assessment (RECIST 1.1 or RANO for HGG) will be considered for purposes of satisfying the primary efficacy endpoint.

Safety and tolerability will be assessed by clinical review of all relevant safety parameters including AEs, physical examinations, laboratory tests, vital signs, ECGs, Lansky Play Score and KPS, dental examination findings, height, and proximal tibial growth plate.

At the end of treatment, each participant will be followed 30 days for the occurrence of AEs/SAEs.

Participants who discontinue lenvatinib treatment for reasons other than radiographic disease progression or initiation of new anticancer therapy will have post-treatment tumor assessments performed every 8 weeks for 24 weeks, then every 12 weeks thereafter until documentation of disease progression or start of a new anticancer agent, whichever occurs first, unless the participant withdraws consent, becomes lost to follow-up, or the study is terminated.

Participants will be followed by telephone every 12 weeks for survival status until death unless the participant withdraws consent, becomes lost to follow-up, or the study is terminated.

Specific procedures to be performed during the study, as well as their prescribed times and associated visit windows, are outlined in the SoA in Section 1.3. Details of each procedure are provided in Section 8.

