8.2.1.2 Tumor Imaging During the Study

The first on-study imaging assessment should be performed the end of Week 8 \pm 7 days. Subsequent tumor imaging should be performed every 8 weeks until Week 24, then every 12 weeks (\pm 7days) thereafter during treatment (or sooner if there is evidence of PD). Imaging timing should follow calendar days from C1D1, and should not be adjusted for delays in cycle starts. Imaging should continue to be performed until disease progression is identified by the investigator, the start of new anticancer treatment, pregnancy, withdrawal of consent, or death, whichever occurs first.

Objective response should be confirmed by a repeat imaging assessment. Tumor imaging to confirm PR or CR should be performed at least 4 weeks after the first indication of a response is observed. Participants will then return to regular scheduled imaging, starting with the next scheduled imaging time point. Participants who receive additional imaging for confirmation do not need to undergo the next scheduled tumor imaging if it is less than 4 weeks later; tumor imaging may resume at the subsequent scheduled imaging time point.

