9.6 Statistical Methods

9.6.1 Statistical Methods for Efficacy Analyses

This section describes the statistical methods that address the primary and secondary efficacy objectives. Methods related to exploratory objectives will be described in the sSAP.

Antitumor activity data will be analyzed by each tumor type. The data cutoff for the primary study analysis for a given tumor type will be determined by the study team, based on the review of data at each interim analysis and predetermined futility guidance.

Only those participants who have measurable disease present at baseline and have their disease re-evaluated at postbaseline visits will be considered evaluable for ORR. These participants will have their response classified according to RECIST 1.1 or RANO for participants with HGG.

Primary Efficacy Analysis

ORR: Objective responses will count only confirmed CR and PR at Week 16. Estimated ORR and its exact 95% CI using the method of Clopper and Pearson will be presented.

Secondary Efficacy Analyses

The BOR will be provided with the descriptive statistics. The ORR, DCR, and CBR will be provided with exact 95% CIs using the method of Clopper and Pearson, and the DOR will be analyzed for responders using Kaplan-Meier approach.

The secondary endpoint of PFS will be analyzed using Kaplan-Meier product-limit estimates. Median PFS and the cumulative probability of PFS at 4, 6, 12, and 24 months will be presented with 2-sided, 95% CIs when an adequate number of at-risk participants at those time points warrant the estimate. The cumulative PFS probabilities will be plotted over time as appropriate.

A summary of the primary analysis strategy for the key efficacy endpoints is provided in [Table 5](#).

Table 5 Table Analysis Strategy for Key Efficacy Variables

Endpoint/Variable	Statistical Method	Analysis Population	Missing Data Approach
Primary Analyses – Within tumor type			
ORR (RECIST 1.1 or RANO for HGG) at Week 16	Summary statistics using Clopper and Pearson method	EAS	Participants in EAS with missing data are considered nonresponders.
Secondary Analyses – Within tumor type			
ORR	Summary statistics using Clopper and Pearson method	EAS	Participants in EAS with missing data are considered nonresponders.
BOR	Summary statistics using Clopper and Pearson method	EAS	Missing observation in EAS population are counted as nonresponders.

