Reviewers will document baseline tumor on post-contrast T1-weighted and T2/FLAIR images. They first identify all lesions, determine whether they are measurable (can be measured), and from these choose target lesions (will be measured throughout the trial). To be considered measurable, a lesion has to show enhancement, have 2 perpendicular diameters ≥ 10 mm, and be suitable for reproducible repeated measurements. Enhancing non-measurable lesions include all other enhancement that is strongly believed to represent tumor, but that does not meet the requirements above. Up to 5 lesions can be selected as target. Selected target lesions are measured, and the sum of products of diameters (SPD) calculated. Enhancing nontarget lesions are identified by location only. Because T2/FLAIR abnormalities are typically more diffuse than tumor enhancement, the T2/FLAIR images will be used for comparison when evaluating later visits, without identification of discrete lesions.

Radiographic response assessment

Target lesion response is determined by the change in the sum of diameters from baseline and from nadir (smallest measurement seen until the visit being evaluated) (Table 8).

Table 8 Target Lesion Response

Response	Definition
Complete Response (CR)	All target lesions have completely disappeared.
Partial Response (PR)	SPD decreased by $\geq 50\%$ from baseline value.
Stable Disease (SD)	SPD $< 50\%$ decreased from baseline, but $< 25\%$ increased from nadir.
Progressive Disease (PD)	SPD increased by $\geq 25\%$ from nadir value.
Non-evaluable (NE)	The sum of diameters cannot be meaningfully evaluated (for example, because of technical factors such as scan quality that obscure one or more target lesions).

Nontarget lesion response is determined by visual inspection of enhancing nontarget lesions collectively and classification into a response category (Table 9).

Table 9 Lesion Response for Enhancing Nontarget Lesions

Response	Definition
Complete Response (CR)	All enhancing nontarget lesions have disappeared completely.
Stable Disease (SD)	Enhancing lesions present, showing no definite growth from the visit where they were smallest.
Progressive Disease (PD)	Unequivocal progression of enhancing lesions (see below).
Non-evaluable (NE)	The sum of diameters cannot be meaningfully evaluated (for example, because of technical factors such as scan quality that obscure one or more target lesions).

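### The neuroblastoma MIBG rule scores a partial response when one lesion clears, however many persist, and its PR, SD and PD categories overlap

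*Combined protocol and SAP*

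**What the plan says.** Section 4.2.1.1 gives neuroblastoma, which sits in the other solid tumors' cohort, its own response scale. The partial response line reads "PR: Resolution of at least 1 MIBG-positive lesion, with persistence of other MIBG-positive lesions". Stable disease is "SD: No changes in MIBG scan in number of positive lesions" and progression is "PD: Development of new MIBG-positive lesions". The outcome is then "combined with RECIST-based efficacy for assessment of the study endpoints".

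The protocol's other written response scale, RANO Table 8 in Appendix 8, sets target-lesion PR at "SPD decreased by $\geq 50\%$ from baseline value".

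Confirmation is required. Section 8.2.1.2 says "Tumor imaging to confirm PR or CR should be performed at least 4 weeks after the first indication of a response is observed", and Section 9.6.1 says "Objective responses will count only confirmed CR and PR at Week 16". The site assessment decides the endpoint in an open-label study. Of central reading, Section 4.1 says only "Images will be collected by a central imaging vendor for possible independent review of response".

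Section 9 does not carry the MIBG rule. Sections 9.4.1 and 9.6.1 name RECIST 1.1 or RANO only, and the Evaluable Analysis Set in 9.5.1 requires measurable disease at baseline. Section 5.1, however, admits neuroblastoma participants who have MIBG-positive disease and no RECIST-measurable lesion.

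**The concern.** A single lesion separates SD from PR, whatever the disease burden. The rule is easiest to meet in participants with the most lesions, where one lesion means least, and no rationale is given for a standard so much looser than RANO's. It allows no tolerance for reading variation at the SD/PR boundary.

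At stake is the neuroblastoma response result. A confirmed one-lesion PR enters ORR and BOR. It also enters the clinical benefit rate without the 23 weeks that 9.4.1 asks of stable disease. Where categories overlap and no precedence is stated, the same scan can be scored as response or as progression.

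**Working it through.** The documents attach no reading-error rate or lesion count to this rule, so there is no plan figure to reproduce. The text is checked first, then illustrated with assumed values.

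**1. Share of disease that earns a PR.** With k lesions at baseline the minimum share cleared is 1/k: 50% (k = 2), 20% (k = 5), 10% (k = 10), 5% (k = 20). RANO's 50% is a size measure (sum of products of diameters), so the comparison is of stringency, not of like units.

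**2. Overlap.** Take five lesions at baseline; one resolves, one appears and four persist.
- PR: at least one has resolved and others persist. Met.
- SD: five before, five after. Met.
- PD: a new lesion. Met.

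No precedence is stated. This step needs no assumed error rate.

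**3. Misread on follow-up, no true change.** Assume each lesion is missed at a reading with probability q = 2% to 5%, independently, with baseline read correctly.
- One reading, at least one lesion missed: 1 − (1 − q)^k. For k = 10 this is 18.3% to 40.1%; for k = 20, 33.2% to 64.2%.
- Confirmed, same lesion missed at both readings: 1 − (1 − q²)^k. For k = 10, 0.4% to 2.5%; for k = 20, 0.8% to 4.9%.
- Confirmed, any lesion missed at each reading: [1 − (1 − q)^k]². For k = 10, 3.3% to 16.1%; for k = 20, 11.0% to 41.2%.

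The text does not say whether the same lesion must be absent twice. If baseline can also be misread, a lesion missed then and seen later is scored as new, hence PD. At k = 20 and q = 5%, baseline is complete with probability 0.95^20 = 0.358, so 41.2% falls to roughly 0.412 × 0.358 = 14.7%, and false PD appears instead.

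**4. Over-call at baseline.** A lesion wrongly called positive at baseline is absent on every later scan, so confirmation does not remove it. Assume 5% of recorded lesions are over-called. The chance of a false PR is 1 − 0.95^k under the current rule, against the binomial probability that at least half the lesions are over-called under a 50% threshold:

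| k | Current rule | At least half cleared |
|---|---|---|
| 2 | 9.8% | 9.8% |
| 3 | 14.3% | 0.7% |
| 5 | 22.6% | 0.12% |
| 10 | 40.1% | 0.006% |

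**5. One response in a small group.** The number of neuroblastoma participants is not given. If it were nine, one such response would move the estimate from 0/9 (Clopper-Pearson 95% CI 0 to 33.6%) to 1/9 = 11.1% (0.3% to 48.2%).

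**6. Other endpoints.** The first scan is at Week 8 ± 7 days, so never before Week 7. SD there already meets the 7-week minimum, and moving a participant from SD to PR leaves disease control unchanged. Duration of response is measured among responders; adding trivial or false ones could lengthen or shorten it.

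**The case against.** **Confirmation.** A reader might infer that any count lower by one is an objective response. It is not: only a response confirmed at least 4 weeks later counts, which deals with most one-off misreads on follow-up. It does not deal with step 4, nor with a genuine, lasting loss of 1 lesion in 20.

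**Expansion.** A reader might infer that one lenient PR could carry neuroblastoma past the none-in-nine futility bar. The Synopsis and Section 4.4 record that enrollment into the other solid tumors' cohort has stopped for insufficient activity, so that consequence no longer applies. Nothing in the documents shows that neuroblastoma reached nine evaluable participants.

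**Entry into ORR.** Read literally, Section 9 classifies response by RECIST or RANO only and leaves MIBG-only participants out of the analysis set. How the two readings combine is also undefined; if both had to agree, a one-lesion MIBG change would not make a response in a participant with measurable disease. This stands as a limit on what can be asserted. It is also a defect in itself: 4.2.1.1 and 5.1 point one way, and 9.4.1, 9.5.1 and 9.6.1 the other.

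**The error model.** Lesion counts and miss rates are assumed. The 41% figure is the top of one reading of an unclear rule and ignores misses at baseline. Net inflation of ORR is not demonstrated.

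**The remedy.** Changing a response rule after open-label data is post hoc. That is a reason to report both versions.

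**Conclusion.** The concern holds in a limited form. On the text alone, the rule lets clearance of 5% of lesions count as a partial response, and its categories are not mutually exclusive. The effect is confined to neuroblastoma ORR, BOR and CBR in participants already enrolled, and it depends on how MIBG is combined with RECIST. Inflation of disease control or of response duration, which a reader might infer, is not supported: the first is essentially unchanged (apart from the overlap case, whose category is undefined), and the direction of the second is unknown.

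The probability of a false confirmed PR runs from 0.4% to 41% over the assumed settings (10 or 20 lesions, 2% to 5% misses, independent readings, baseline read correctly), depending mainly on whether the same lesion must be absent twice. The width of that range shows that the rule is underspecified; it is not an estimate of bias. A change is worth making, but it does not bear on whether the cohort was rightly closed.

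**What to change.** For efficacy scoring only, amend the MIBG criteria in 4.2.1.1:
- **PR:** a proportional threshold, for example at least a 50% reduction from baseline in the number of MIBG-positive lesions, with no new lesion.
- **SD:** any change short of PR, without a new lesion.
- **PD:** takes precedence over PR and SD when a new lesion is present.
- **Combination:** state how MIBG and RECIST readings combine when they disagree.

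Reconcile 4.2.1.1 and 5.1 with the ORR definition in 9.4.1, the analysis set in 9.5.1 and the evaluability text in 9.6.1, so that it is clear whether MIBG-only participants are analysed.

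Score the enrolled neuroblastoma participants under the new rule from existing scans. Report the result under the current rule beside it, because the change comes after open-label data.

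Cost: wording in a few sections and no new scans. Some scans may need their lesion counts extracted, since the documents do not say that counts were recorded. The neuroblastoma ORR may be slightly lower. Nothing changes for participants with two lesions and no new one, where one lesion is already half.
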